## Protocol & Statistical Analysis Plan

Patients in the third trimester that present to the obstetrical triage for assessment of labor (contractions or rupture membranes) as well as patients admitted for labor and delivery will be approached. After informed consent is obtained, [name] or I will perform a transperineal ultrasound (TPUS) using the glove-covered Butterfly iQ+. An independent, blinded examiner will then perform a traditional digital cervical exam (DCE). The study PI's will be blinded to the DCE measurement until the end of the study. The patient will act as their own control. The patient will then be asked to score discomfort on a scale of 0-3 and preference for a method, if any. After 30 patients are enrolled, the PI's will compare the TPUS dilation measurements to the DCE dilation measurements and calculate a simple correlation. The discomfort scale will be analyzed using a Wilcoxon Signed Rank test.

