### Exclusion Criteria:

Second trimester (less than 28 weeks) BMI>50 Does not wish to participate

Patients in the 3rd trimester that require a digital cervical exam (DCE) for assessment of labor will be approached. After informed consent is obtained, one of two study investigators will perform a transperineal ultrasound (TPUS) using the glove-covered Butterfly iQ+ probe. The Butterfly iQ+ does not have a transperineal probe or setting, therefore, the "bladder" preset setting will be used. The "bladder" setting has been predetermined to provide the best cervical images. This pocket ultrasound is FDA-approved and is the standard of care for point of care ultrasounds in many institutions and is already used in our department. The TPUS will be performed by 1 of the 2 investigators with digital calipers. There will be 3 measurements: dilation, effacement, and station. The dilation measurements will be made from the inside margins of the cervix. Effacement will be measured by marking the thinnest and most easily imaged lip of the cervix. Zero station will be assumed to be 5 cm above the perineum, with distances from 6-10 cm corresponding to -1 to -5 station clinically. An independent, blinded examiner will then perform a traditional digital cervical exam, which will be recorded in EPIC. The study investigators will be blinded to the DCE measurement until the end of the study. The patient will act as their own control. Additionally, we will collect EGA, race, ethnicity, age, BMI, and indication for assessment of the

cervix. The patient will then be asked to score discomfort on a scale of 0-3 (none-extremely). They will then be asked to state if they preferred the TPUS, DCE or have no preference. At the end of the study the TPUS exams will be compared to the DCE, and a simple correlation will be calculated.

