### **Data Analysis**

We chose a simple correlation  $r$  ( $r=0.5$ ). Using a two-tailed test, 5% significance level test ( $\alpha=0.05$ ) with power 80% power ( $\beta=0.2$ ), the required sample size is approximately ( $n=29$ ).

For the primary outcome, we will use the two-tailed test. For the secondary outcome (patient experience), we will use the Wilcoxon Signed Rank test.

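### Discomfort and preference are asked only after both exams in a fixed TPUS-then-DCE order, so the patient-experience comparison mixes method with order and recall

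*Combined protocol and SAP*

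**What the plan says.** The procedure is described twice in the combined protocol and SAP: in the overview (section Protocol & Statistical Analysis Plan) and in the fuller text under Exclusion Criteria. Both give the same sequence.

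- **First exam:** "After informed consent is obtained, one of two study investigators will perform a transperineal ultrasound (TPUS) using the glove-covered Butterfly iQ+ probe".
- **Second exam:** in the overview, "An independent, blinded examiner will then perform a traditional digital cervical exam (DCE"); in the fuller text, "An independent, blinded examiner will then perform a traditional digital cervical exam, which will be recorded in EPIC".
- **Ratings:** "The patient will then be asked to score discomfort on a scale of 0-3 and preference for a method, if any". The fuller text puts the preference question last: "They will then be asked to state if they preferred the TPUS, DCE or have no preference".
- **Control:** "The patient will act as their own control".
- **Secondary analysis** (Data Analysis): "For the secondary outcome (patient experience), we will use the Wilcoxon Signed Rank test".
- **Primary analysis** (overview): "After 30 patients are enrolled, the PI's will compare the TPUS dilation measurements to the DCE dilation measurements and calculate a simple correlation".

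Neither description mentions a randomised or alternated order, a discomfort score between the two exams, or an order term in the analysis. A paired test needs one score per exam; the text implies this but does not say it outright.

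**The concern.** A within-patient comparison removes differences between patients. It does not remove effects of sequence. Two separate effects are possible here.

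1. **Order.** A second exam may be rated differently because it is second, whichever method it is. With one sequence only, that effect has the same sign in every pair and adds directly to the method difference.
2. **Recall and contrast.** Both ratings are taken after the DCE. The DCE score is fresh, while the TPUS score is remembered and may be set against the exam just completed. The preference question has the same weakness.

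At stake is a claim such as less discomfort with TPUS, or TPUS preferred. Such a result could arise partly or wholly from sequence. A real method difference could equally be hidden if the order effect runs the other way.

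**Working it through.** **The plan's own figure.** Data Analysis states r = 0.5, two-sided alpha 0.05, 80% power and n = 29. By Fisher's z:

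n = ((1.960 + 0.842) / atanh(0.5))² + 3 = (2.802 / 0.5493)² + 3 = 29.01.

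The stated figure reproduces (power 80.0% at 29, 81.4% at the 30 to be enrolled). It concerns the primary correlation and does not depend on exam order.

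**What the paired difference estimates.** Let D = DCE score minus TPUS score, m the method effect, o the effect of being second, and c the change in D caused by rating TPUS from memory after the DCE.

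| Design | Expected D |
|---|---|
| As planned (fixed order, both scores at the end) | m + o + c |
| Fixed order, each score straight after its own exam | m + o |
| Half in each order, each score straight after its own exam | ½(m + o) + ½(m − o) = m |

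No sample size separates m from o in the first two rows, because no patient has the DCE first. The second row does remove c.

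**Primary outcome.** If being second, or a delay, adds the same constant k to every DCE dilation, then corr(X, Y + k) = corr(X, Y). The correlation is unchanged.

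**Illustrative size, first model.** All inputs except the 30 pairs and the 0-3 scale are assumptions: patient level N(mean 1.2, SD 0.7), per-exam noise SD 0.5, rounding and clipping to 0-3, no true method difference, and a shift added to the second exam. The test is the signed-rank with zeros dropped, normal approximation, two-sided 5%, with 4,000 trials per setting.

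| Shift (points) | Significant, fixed order |
|---|---|
| 0 | about 5% |
| 0.1 | about 9% |
| 0.2 | about 24% |
| 0.3 | 46% to 48% |
| 0.5 | about 89% |

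The range at 0.3 is simulation error between runs. With 15 patients in each order the rate stayed at about 5% or below.

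The noise SD matters as much as the shift. For a 0.3-point shift under fixed order:

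| Noise SD | Significant |
|---|---|
| 0.3 | 72% |
| 0.5 | 48% |
| 0.8 | 23% |
| 1.0 | 17% |

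**Second model, as a check.** This uses latent normal scores cut into four categories with an assumed within-patient correlation of 0.5. Order effects of 0, 0.25, 0.5 and 0.75 latent SD gave 5%, 22%, 65% and 93% under fixed order, and 5%, 4%, 3% and 2% with 15 in each order. With a method effect of +0.5 SD and an order effect of −0.5 SD, rejection was about 5% under fixed order and 55% when balanced, so masking is as possible as a spurious finding.

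**The case against.** The strongest defence is that TPUS-first serves the primary outcome. The investigators who place the calipers must stay blind to the DCE result until the study ends. With TPUS first, no DCE result exists when the reading is made, so the order itself guarantees blinding. With DCE first, the result would already be in EPIC and could be repeated by the patient; keeping the operator out of the room deals with neither. Coordinating two examiners in either order on a labor unit is also harder than preparing envelopes. This stands. It makes randomised order a debatable trade-off, and the fixed order is not an error.

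Three further points also stand:

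- **The test remains valid for what it tests.** A reader might infer that a fixed order invalidates the signed-rank test. It does not: the test still assesses whether the paired scores differ. What is lost is attributing that difference to method.
- **The simulated rates are conditional.** They assume no true method difference and depend on an assumed shift and noise SD. In the first model, a true 0.5-point method difference with no order effect is detected about 88% of the time under either design. If the first exam were scored worse, the fixed order would work against TPUS.
- **The scope is narrow.** A reader might infer that the whole TPUS-DCE comparison is confounded, dilation included. The planned primary analysis is a correlation, which a uniform shift does not move, and the documents give no delay between exams from which to argue otherwise.

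The defence does not cover the timing of the scores. Blinding the TPUS operator to the DCE gives no reason to postpone the TPUS discomfort score until after the DCE.

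**Conclusion.** The point holds for the secondary patient-experience outcome only. That method and order cannot be separated follows from the design and needs no assumption. That the TPUS score is a recalled rating follows from the stated sequence. Whether an order or contrast effect exists, and which way it runs, is unknown: the documents give no effect size, direction or variance. The illustrative rates (about 9% to 89% for shifts of 0.1 to 0.5 points at noise SD 0.5; about 17% to 72% for a 0.3-point shift as noise SD falls from 1.0 to 0.3) show that modest effects could matter with 30 pairs. They do not predict this trial's error rate.

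The documents support neither the reading that the primary result is biased by order nor the reading that order must be randomised. They do support changing when the scores are taken and how the result is worded. This is worth doing because it is cheap, but it does not threaten the trial's main conclusion.

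**What to change.** In both descriptions of the procedure (the overview and the text under Exclusion Criteria):

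1. Take the 0-3 TPUS discomfort score immediately after the TPUS and before the DCE begins.
2. Take the 0-3 DCE discomfort score immediately after the DCE.
3. Ask for preference last.

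In Data Analysis, add a sentence such as: *The signed-rank result and the stated preference apply to TPUS performed before DCE; exam order was fixed, so order and method effects cannot be separated.*

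**Cost:** one extra moment of questioning per patient and a narrower conclusion. No added staff or exams, and no loss of blinding. The change keeps the TPUS score from being coloured by the later DCE. It does not remove the order effect, and preference is still asked after both exams.

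**Optional:** randomise or alternate the order, for example 15 patients each way. Do this only if the sponsor judges that the TPUS operator can be kept blind to a DCE already recorded. It would remove the order effect from the average difference, at the price of a weaker guarantee on the primary reading and more coordination.

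### The only planned TPUS-versus-DCE analysis is a simple correlation, which ignores bias and does not express disagreement in centimetres

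*Combined protocol and SAP*

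**What the plan says.** The section Protocol & Statistical Analysis Plan describes a paired comparison: TPUS is done first, a blinded independent examiner then performs the DCE, and each woman serves as her own comparison. After 30 women, "the PI's will compare the TPUS dilation measurements to the DCE dilation measurements and calculate a simple correlation". The procedures text under Exclusion Criteria repeats this: "At the end of the study the TPUS exams will be compared to the DCE, and a simple correlation will be calculated".

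Data Analysis gives the sizing: "We chose a simple correlation" with r = 0.5, "Using a two-tailed test", a "5% significance level test" and 80% power, for which "the required sample size is approximately" 29. It adds: "For the primary outcome, we will use the two-tailed test". The test is not named further; from context it is the test of the correlation.

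Nowhere do the documents plan a mean difference, limits of agreement, a concordance or intraclass coefficient, a share of pairs within a stated distance, an acceptable difference or a success criterion. The Wilcoxon Signed Rank test applies to patient experience only.

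**The concern.** When two methods measure the same quantity in the same women, the useful question is how far apart the readings are. A correlation answers a different one: whether the readings rise together along some straight line. It falls short in three ways.

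- **Bias.** It is unaffected by a constant offset or a change of scale.
- **Scatter.** It does fall as scatter grows, but a test against zero can be passed with very wide scatter, and r is not in units of dilation.
- **Case mix.** For the same measurement error, r rises with the spread of dilation in the sample. Triage patients and women admitted for labor are pooled, which would widen that spread if the groups differ in dilation.

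This is the only analysis of TPUS against DCE. Carried out as written, the study could report a significant correlation whether TPUS is close to DCE or systematically away from it, and a reader could not tell which.

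**Working it through.** **Inputs from the documents:** r = 0.5, two-sided α = 0.05, power 80%, stated n about 29 (Data Analysis); 30 women measured by both methods (Protocol & Statistical Analysis Plan).

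**Assumptions, not in the documents:** dilation recorded in cm by both methods; between-woman SD of 1.5 to 2.5 cm, equal for both methods.

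**1. The plan's own figure.** Fisher's z for a test against r = 0:

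n = ((1.960 + 0.842) / atanh(0.5))² + 3 = (2.802 / 0.5493)² + 3 = 29.01.

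The stated 29 is reproduced, so the null value is r = 0. Approximate power is 80.0% at 29 and 81.4% at 30. The arithmetic is right for this test.

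**2. What counts as significant.** The critical value is r = t / √(n − 2 + t²). With n = 30, t(28) = 2.048, so r = 2.048 / √(28 + 4.196) = 0.361.

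**3. Disagreement compatible with a given r.** With equal SDs and no bias, the SD of the differences is SD × √(2(1 − r)), and the 95% limits of agreement are ±1.96 times that.

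| r | Limits in SD units | SD 1.5 cm | SD 2.0 cm | SD 2.5 cm |
|---|---|---|---|---|
| 0.361 (just significant) | ±2.22 | ±3.32 | ±4.43 | ±5.54 |
| 0.5 (design value) | ±1.96 | ±2.94 | ±3.92 | ±4.90 |
| 0.8 | ±1.24 | ±1.86 | ±2.48 | ±3.10 |

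Over a wider assumed SD of 1 to 3 cm, the limits at r = 0.5 run from ±1.96 to ±5.88 cm.

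**4. Bias.** Suppose TPUS = 0.5 × DCE + 1. Then r = 1.00, yet at a DCE of 8 cm TPUS reads 0.5 × 8 + 1 = 5 cm, which is 3 cm lower. A simulation of 10,000 trials (n = 30, true r = 0.5, assumed SD 2 cm) shows the same for the planned test:

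| TPUS behaviour | Chance of a significant correlation | Mean concordance coefficient |
|---|---|---|
| No bias | 82.9% | 0.48 |
| 2 cm too high in every woman | 82.9% | 0.33 |
| Compressed to half scale | 82.9% | 0.39 |

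The first column of results is constant by algebra, not by chance. The concordance coefficient does respond.

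**5. Case mix.** Fix the SD of the differences at 1.5 cm, with error shared equally, so each method's error variance is 1.5² / 2 = 1.125. Then r = true variance / (true variance + 1.125). For a true SD of 1 cm, r = 1 / 2.125 = 0.47. For 2.5 cm, r = 6.25 / 7.375 = 0.85. The differences have the same spread in both cases.

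**6. Precision of an agreement analysis at n = 30.** With t(29) = 2.045:

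- Mean difference: 2.045 / √30 = 0.37 SD of the differences.
- Each limit: 2.045 × √(1/30 + 1.96²/58) = 0.65 SD of the differences.

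At r = 0.5 the SD of the differences equals the dilation SD. For 1.5 to 2.5 cm the half-widths are therefore about 0.56 to 0.93 cm for the mean difference and 0.97 to 1.61 cm for each limit.

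**The case against.** The strongest reply is that the documents never state an aim of agreement or of replacing DCE, and set no pass mark. On that view the plan is being held to a goal it does not claim, and r = 0.5 is only a sizing value. It is true that no aim or threshold is written, so any talk of a successful result is inferred from the significance test. But the plan does set out to compare the two dilation measurements, and the correlation does not tell the reader how they compare in size.

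Other points stand as limits on the concern:

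- Correlation does respond to scatter. The complaint is that the bar is low and the result is not in cm.
- Centimetres are stated only for station. Reading dilation in cm is natural but assumed.
- No dilation distribution is given, so the SD range and the effect of pooling are assumptions, and the half-scale example is an illustration rather than a predicted error.
- DCE is not a perfect reference. With one reading per method, limits of agreement combine both methods' errors and cannot assign them to TPUS.
- The figure of 29 was derived for the correlation and does not justify an agreement analysis.

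The paired readings will be collected anyway, so nothing is lost irreversibly. That makes the change cheap; it does not make the planned analysis adequate.

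**Conclusion.** The concern holds, and the primary analysis is wrong as written for a paired method comparison. Its blindness to a constant offset or scale error is algebraic and needs no assumption. The size of the scatter that could pass depends on the assumed SD, equal SDs and no bias: ±2.9 to ±4.9 cm at the design value of r, and still ±1.9 to ±3.1 cm at r = 0.8. The sample-size calculation is correct for its own test; the fault lies in the choice of statistic.

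**What to change.** Before the investigators are unblinded to the DCE readings, amend the plan as follows.

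- **Primary analysis:** the mean TPUS minus DCE difference in dilation and the 95% limits of agreement (Bland-Altman), each with a 95% CI. State the unit of dilation.
- **Criterion:** an acceptable difference, specified and justified by the sponsor. The documents give none, and without one any limits could be called favourable.
- **Supporting analyses:** Lin's concordance coefficient or an absolute-agreement intraclass correlation, with CI; the percentage of pairs within a stated distance, for example 1 cm, with the choice justified; and a regression of the difference on the mean to check for proportional bias.
- **Correlation:** report it as supportive only.
- **Sample size:** replace the rationale for 29 with the precision expected from 30 pairs, ±0.37 SD of the differences for the mean difference and about ±0.65 for each limit.

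The cost is revised wording and a few lines of analysis on the same 30 pairs, with no new data or patients. If the sponsor finds that precision too low for the acceptable difference it sets, more pairs would be needed; at n = 100 the half-widths would be 0.20 and 0.34. A target sample size cannot be derived from the documents, which give neither an SD nor an acceptable difference.

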### Inclusion Criteria:

Pregnant women in the third trimester presenting for assessment of labor or admitted for labor and delivery.

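### The plan compares TPUS with DCE dilation only by a simple correlation, which cannot show how many centimetres the two readings differ

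*Combined protocol and SAP*

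**What the plan says.** The opening section (Protocol & Statistical Analysis Plan) says that after 30 patients the investigators will "compare the TPUS dilation measurements to the DCE dilation measurements and calculate a simple correlation". The procedures text under Exclusion Criteria repeats this: "the TPUS exams will be compared to the DCE, and a simple correlation will be calculated". Data Analysis begins "We chose a simple correlation", gives r = 0.5, a "5% significance level test", 80% power and about 29 patients, and adds: "For the primary outcome, we will use the two-tailed test". The Wilcoxon signed rank test is assigned to discomfort, not to the readings.

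The population is mixed. Inclusion Criteria admits "Pregnant women in the third trimester presenting for assessment of labor or admitted for labor and delivery", and the opening section confirms that besides triage patients, "patients admitted for labor and delivery will be approached". No quota, stratification or adjustment by setting is given. The procedures text says "we will collect EGA, race, ethnicity, age, BMI, and indication for assessment", but gives the indication no role in the analysis.

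No section names a mean difference, limits of agreement, a concordance or intraclass coefficient, or an acceptable difference between the readings. The opening section ties the correlation to dilation. The procedures text also measures effacement and station, but names no further statistic for them.

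**The concern.** Each patient is read by both methods and serves as her own control. Such a design can answer how far the TPUS reading lies from the DCE reading, in centimetres. A correlation does not answer that. It measures how closely the points follow some straight line, not how close they lie to the line of equality. An ultrasound reading that is always 2 cm low, or always half the digital one, gives the same r as a perfect one. The device has no transperineal setting and a different preset is used, so a systematic offset deserves a check.

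The study could therefore report a significant correlation at its planning value while the two readings commonly differ by several centimetres, and nothing in the planned output would show it. A lesser point is that r depends on the spread of dilation in the sample, and so on who happens to be enrolled.

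**Working it through.** **1. The plan's own figure.** Inputs from Data Analysis: r = 0.5, two-sided alpha 0.05, power 80%. The null is not written out and is taken as zero correlation. With Fisher's z:

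n = ((1.960 + 0.842) / atanh(0.5))² + 3 = (2.802 / 0.549)² + 3 = 29.01.

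The stated 29 is reproduced. Power is 80.0% at n = 29 and 81.4% at n = 30. At n = 30 the smallest significant |r| is 0.361, and an observed r of 0.5 has a 95% CI of 0.17 to 0.73. The sample size is right for the test it serves.

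**2. What r leaves out.** For any constants a and b > 0, corr(a + b·TPUS, DCE) = corr(TPUS, DCE). Checked numerically, readings 2 cm low throughout and readings at half scale both give r = 1 against the true values.

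**3. What r = 0.5 implies about the differences.** Take the simple correlation as Pearson's and both readings as recorded in cm. Let D be the DCE SD and T the TPUS SD.

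Var(TPUS − DCE) = T² + D² − 2rTD.

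This is smallest at T = rD, where it equals D²(1 − r²). With r = 0.5:

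- SD of the differences ≥ √0.75 × D = 0.866 D
- half-width of the 95% limits of agreement ≥ 1.96 × 0.866 D = 1.70 D

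The minimum needs no error model. If the two methods have equal SDs, the SD of the differences is D√(2(1 − 0.5)) = D and the half-width is 1.96 D.

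The documents give no dilation SD, so D is assumed. The range comes from within-setting SDs of 1 cm (triage) and 1.5 cm (admitted), a 50:50 mix, and a gap in mean dilation of 0 to 4 cm: D² = (1² + 1.5²)/2 + gap²/4 = 1.625 + gap²/4.

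| Gap (cm) | D (cm) | Minimum half-width (cm) | Half-width, equal SDs (cm) |
|---|---|---|---|
| 0 | 1.275 | 2.16 | 2.50 |
| 2 | 1.620 | 2.75 | 3.18 |
| 3 | 1.969 | 3.34 | 3.86 |
| 4 | 2.372 | 4.03 | 4.65 |

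These widths lie either side of the mean difference, whose size r does not reveal.

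**4. Dependence on spread (illustration only).** Same assumptions, with TPUS = DCE + random error of SD 2 cm. The limits are always ±1.96 × 2 = ±3.9 cm around the mean difference. Pooled r = √(D²/(D² + 4)) is 0.54, 0.63, 0.70 and 0.76 at gaps of 0, 2, 3 and 4 cm. The closeness of the readings is unchanged while r moves.

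The effect of the mix is uneven. At a 3 cm gap, r is 0.70 at 15:15 and 0.70 at 10 triage to 20 admitted. It is 0.67 at 5:25 and 0.62 at 25:5. Part of the last drop comes from a lower within-setting correlation (0.54 to 0.48), because most patients are then in the group with the smaller SD.

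**5. Precision of the added estimates.** 95% CI half-widths, in SDs of the differences:

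- mean difference, n = 30: 2.045/√30 = 0.37
- each limit, n = 30: 2.045 × √(1/30 + 1.96²/58) = 0.65
- each limit, n = 15: 2.145 × √(1/15 + 1.96²/28) = 0.97

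**The case against.** The strongest reply is that the plan defines one population, triage plus admitted, and promises nothing about tracking within either setting. Enrolling across a range of dilation is legitimate, every correlation depends on range, and the test of zero correlation is valid. All of that stands. It limits the case-mix point to a caveat but does not touch the point about differences in centimetres.

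A reader might infer several stronger things that the documents do not support:

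- *Pooling inflates r by a known amount.* Holding pooled r at 0.5 under the assumptions above gives a within-setting r of 0.41, 0.35 and 0.30 at gaps of 2, 3 and 4 cm. But this requires the TPUS error SD to rise to 2.8, 3.4 and 4.1 cm, so it describes three progressively worse devices rather than one device under different mixing. At gaps of 0 and 1 cm the within-setting r is 0.50 and 0.47. The documents give no gap, mix or SD.
- *A significant r could arise with no within-setting association.* That would need TPUS readings to shift with setting without following dilation inside it. The documents do not exclude this, but nothing in them suggests it.
- *r = 0.5 is a success threshold, or the study claims that TPUS can replace DCE.* Data Analysis uses 0.5 only to size the study, and no section makes a replacement claim.

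A setting-adjusted correlation would also settle little at this size. An adjusted r of 0.30 has a 95% CI of about −0.07 to 0.60, which overlaps heavily with 0.17 to 0.73 for a pooled r of 0.5.

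Finally, the plan does say that readings will be compared, which could cover more than r. But no other statistic is named for them.

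**Conclusion.** The concern holds for agreement. Followed as written, the plan can show that TPUS and DCE dilation are associated but not how many centimetres they differ. That conclusion needs no assumption about case mix, because a correlation ignores offset and scale. The bound of 1.70 DCE SDs at r = 0.5 is algebra for Pearson's r; its translation to about ±2.2 to ±4.0 cm rests on an assumed DCE SD of 1.275 to 2.372 cm. Reading the limits as covering about 95% of differences also assumes roughly normal differences.

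The dependence of r on the triage/admitted mix is a caveat on interpretation that the documents do not allow anyone to size. The primary test and its sample size are not in question.

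**What to change.** Keep the pooled correlation as the primary analysis. Add to Data Analysis, before the investigators are unblinded to the DCE readings:

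- the mean TPUS-minus-DCE dilation difference and the 95% limits of agreement, each with a 95% confidence interval, over all patients;
- a statement that any conclusion about how closely TPUS matches DCE will rest on these differences and not on r alone.

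Optionally, record setting (triage or admitted) with the indication already collected, and display the differences by setting as description only.

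The cost is a few lines of text and a little more analysis on the same 30 pairs, with no extra patients or procedures. Precision is limited. If the SD of the differences were 2 cm, the mean difference would carry a 95% CI of about ±0.75 cm (0.37 × 2) and each limit about ±1.3 cm (0.65 × 2). By-setting limits would be looser still, at 0.97 SD with 15 patients, and the plan does not guarantee that number in either setting.
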